#### Clinical examination

Height:                      Weight:                      ASA:                      PS:  
Vitals                      BP                      Pulse                      Temperature                      Saturation                      RF

Pulmonary stethoscopy

Cardiac stethoscopy

Abdomen

Rectal examination:

Gross neurological examination:

Date                      Place

Clinical examiner:

## Appendix 4 – Endoscopy 1, Phase I and II

Patient name:

Date:

Endoscopic PDAI to be filled in:

Criteria	Score	Patient score
Endoscopy		
Endoscopic inflammation		
Edema	1	
Granularity	1	
Friability	1	
Loss of vascular pattern	1	
Mucous Exudate	1	
Ulceration	1	
Total	6	

Endoscopy complications: \_\_\_\_\_

Did the patient receive analgesia/sedation

No

Yes, which: \_\_\_\_\_

Biopsies taken for histology: \_\_\_\_\_

Biopsies taken for microbiology: \_\_\_\_\_

GM-CSF Metronidazole/Fosfomycin applied: \_\_\_\_\_

Medical complications: \_\_\_\_\_

Date                      Place

Endoscopy physician:

## Appendix 5 – Endoscopy 2, Phase I and II

Patient name:

Date:

Date of application of GM-CSF metronidazole/Fosfomycin:

Endoscopic PDAI to be filled in:

Criteria	Score	Patient score
Endoscopy		
Endoscopic inflammation		
Edema	1	
Granularity	1	
Friability	1	
Loss of vascular pattern	1	
Mucous Exudate	1	
Ulceration	1	
Total	6	

Endoscopy complications: \_\_\_\_\_

Did the patient receive analgesia/sedation

No

Yes, which: \_\_\_\_\_

Biopsies taken for histology: \_\_\_\_\_

Biopsies taken for microbiology: \_\_\_\_\_

Date                      Place

Endoscopy physician:

Protocol code no: 2020-01-GMF-1  
EudraCT no: 2020-000609-10

## Appendix 6 – Histology

Patient name:

Date:

Histological PDAI to be filled in:

Criteria	Score	Patient score
Histology		
Acute histological inflammation		
Polymorphonuclear leucocyte infiltration		
Mild	1	
Moderate + crypt abscess	2	
Severe + crypt abscess	3	
Ulceration per low power field (mean)		
<25%	1	
25-50%	2	
>50%	3	
Total	6	

Date                      Place

Pathologist:

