### **Bias**

This study is an open-label proof-of-concept study with a single treatment arm. There is no blinding of patients or the investigator. The only blinded examination is the pathology examination of mucosal biopsies of the pouch and 16S rRNA sequencing. The pathologist is unaware of whether samples are taken before the application of the study drug or after. Therefore, the histology of the PDAI should not be influenced by bias.

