### **Special assays or procedures**

#### **Histology**

Two biopsies of 2 mm in size each will be taken for assessment of inflammation of the mucosa, according to the PDAI. Biopsies will be fixed in a 4% neutral buffered formaldehyde ('formalin') solution. Biopsy samples will be prepared in sections of FFP (formalin fixed paraffin) wax-embedded tissue, for histology with routine HE (hematoxylin/eosin)-staining. A trained pathologist will review the samples, without prior knowledge of the patient's clinical or treatment status.

Biopsies are reported descriptively and using the PDAI. They will assess the quantity of acute and chronic inflammation, presence of crypt abscesses, erosions and ulcers as well as loss of villous height, granulomas and dysplasia. Chronic inflammatory changes will be distinguished from true pouchitis, as the mucosa of the healthy pouch undergoes adaptive changes after surgery. These changes, which are also frequently described as 'colonic metaplasia' include villous atrophy, crypt hyperplasia, infiltration of the lamina propria of mononuclear cells, eosinophils and histiocytes (68).

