## 9. Data collection, handling and quality assessment

In accordance with Danish law on personal data, we have approval for this trial from Region Sjælland through their data application system (REG-106-2020). Data handling will be in accordance with legislation on the processing of sensitive personal information, the GDPR (General Data Protection

Regulation) and the Data Protection Act. We will also seek approval for the trial from The National Committee of Health Research Ethics and the Danish Medicines Agency.

Data from each patient will be recorded continuously and written in forms prepared before the trial begins. Appendix 3-6 and 8 are considered CRF on which source data is directly recorded. During the recruitment meeting, we will use paper work sheets for baseline data and inclusion/exclusion criteria. During the therapeutic endoscopy, we will use paper work sheets for data collection; afterwards data will be entered into an electronic database using the Easytrial platform. All other data will be recorded directly to the electronic Easytrial database. The paper work sheets will be stored in an identifiable manner in a locked cabinet at the respective research sites. All collected data will have source documentation.

Data will be stored as personally identifiable for 10 years, after which they are deleted on December 31, 2030. Data will be stored in compliance with GDPR and at EasyTrial (secure data storage). According to the Danish Medicines Agency, data from a clinical trial involving study medicine, must be stored for a minimum of 5 years after conclusion of the trial. This is necessary in case a potential reexamination of the data is needed.

If a patient withdraws from the study, the collected data will be anonymized. If the patient requests the collected data to be deleted, this will be done.

Data will be handled by [name] and [name] and access to EasyTrial will be restricted solely to them. The investigators will be allowed direct access to data and documents, among these the patients' medical records.

The trial will be monitored by the Good Clinical Practice Unit of the University of Copenhagen. During the duration of this trial, they will also have access to the data we collect. Similarly, the Danish Medicines Agency, according to section 90(2)-5 of the Danish Medicines Act, and The Danish Data protection Agency can conduct inspection visits and get access to the data.

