### **Storage of biological material**

During the trial, biological material will be stored in a research biobank especially set up for this study. The use of a research biobank is to ensure that differences in analyses from patient to patient will be minimal. The research biobank will be reported to the Region Sjælland, and will be maintained using their regulations.

The biopsies are each 2 mm in diameter. The biological material will be stored in an identifiable fashion through a patient code (pseudo-anonymous, as the CPR (Civil Person Registry) number will be stored in a key-file at EasyTrial). Frozen samples will be stored according to the local protocol.

After the cutting of the FFPE blocks containing the biopsy specimens collected from the pouch, these blocks will be returned to the respective pathological archives. Both the biological material (stained glass slides and FFPE blocks of biopsies) and the key-file will be stored until conclusion of the clinical trial, after which both the key-file and the biopsy samples are destroyed.

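### The pathologist is said to be blind to before/after status, but the histology form carries patient name and a date, and no described procedure secures the blind

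*Protocol*

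**What the plan says.** The Bias paragraph in section 3 of the protocol describes an open-label, single-arm study and then makes an exception: "The only blinded examination is the pathology examination of mucosal biopsies of the pouch and 16S rRNA sequencing". It goes on: "The pathologist is unaware of whether samples are taken before the application of the study drug or after". From this it concludes: "Therefore, the histology of the PDAI should not be influenced by bias". The Histology paragraph in section 7 repeats the claim: "A trained pathologist will review the samples, without prior knowledge of the patient's clinical or treatment status".

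Appendix 6 is the histology scoring form. It opens with fields for the patient's name and a date, gives the instruction "Histological PDAI to be filled in", and closes with a date-and-place line and a pathologist signature line. Section 9 gives the form its standing: "Appendix 3-6 and 8 are considered CRF on which source data is directly recorded".

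On specimens, the section on storage of biological material says: "The biological material will be stored in an identifiable fashion through a patient code". The key to that code is held in the EasyTrial database.

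**The concern.** In Phase I, biopsies are taken on Day 1 and about Day 7. In Phase II, they are taken on Day 1 and about Day 14. A reader who sees a patient's name and the sampling date on two forms knows which sample came first, and so which one preceded the drug. That is the knowledge the Bias paragraph says the reader lacks.

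The trial has no control arm, so a tendency to score later slides more favourably cannot be separated from a treatment effect. The clinical and endoscopic parts of the PDAI are scored open-label, which leaves histology as the only PDAI component for which the plan claims protection. It contributes to the Phase II primary outcome, and a 3-point fall in the histological score is itself a secondary outcome.

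**Working it through.** The plan states no figure for this point, so there is none to reproduce. The check has two parts.

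**1. The claim set against the described procedure**

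| Question | What the protocol gives |
|---|---|
| Is the pathologist said to be blind to before/after? | Yes, in Bias (section 3). Histology (section 7) adds treatment status. |
| What identifies the case on the scoring form? | Patient name and a date (Appendix 6) |
| Is the form the source record? | Yes (section 9) |
| Does the stored-sample code hide the visit? | No. It is a patient code, so it hides identity, and a form asking for the name undoes even that. |
| Is there a masked specimen number, a random reading order or batch reading? | None described |
| What is the header date? | Not defined |

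The header date can be read in two ways.

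- *Biopsy date.* Two forms with one name and two dates show the order directly. A separate date line beside the signature makes this reading plausible, but it is an inference.
- *Reading date.* If slides are read as they arrive, the reading dates follow the sampling order and the name links the pair. The protocol requires no other order.

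**2. How much could depend on it**

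PDAI maxima from Appendix 1:

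- clinical: 2 + 1 + 2 + 1 = 6
- endoscopic: 6 × 1 = 6
- histological: 3 + 3 = 6

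The total is 18, which matches Appendix 7. Histology is 6/18 = 33%, and the other 12 points are open-label. Because the histological part spans 6 points, a fall of 3 could in principle come from histology alone.

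The illustration below needs two inputs that the protocol does not give. They are assumed here: the SD *s* of the total PDAI change (2 to 3), and a mean favourable drift *d* on post-treatment slides (0.5 or 1 point), with no true effect.

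Chance per patient of a fall of 3 or more, with the total rounded to whole points: P = 1 − Φ((2.5 − d)/s).

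- s = 2.5, d = 0: 1 − Φ(1.0) = 15.9%
- s = 2.5, d = 0.5: 1 − Φ(0.8) = 21.2%
- s = 2.5, d = 1: 1 − Φ(0.6) = 27.4%

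The next table gives the rejection rate of a two-sided 5% signed-rank test at n = 12. It comes from 100,000 simulated trials per cell, with normal untied changes. The exact rule rejects when the smaller rank sum is 13 or less, which has a true size of 4.2%.

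| Drift | SD 3 | SD 2.5 | SD 2 |
|---|---|---|---|
| 0 | 4.2% | 4.2% | 4.2% |
| 0.25 | 4.9% | 5.3% | 5.8% |
| 0.5 | 7.1% | 8.4% | 10.8% |
| 1 | 15.8% | 21.3% | 31.5% |

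Rounding changes to whole points and using the normal approximation (8,000 trials per cell) raises these by up to about 2 percentage points, to 12.1% and 33.2% at the top of the last two rows.

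**The case against.** The strongest reply is that nothing here shows the pathologist is unblinded.

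- Appendices 4 and 5 are labelled as first and second endoscopy, and Appendix 5 asks when the drug was given. Appendix 6 is a single generic form with no visit label and no treatment date. A first form on its own reveals nothing.
- The protocol does not say who fills in the header. Section 9 limits paper sheets to the recruitment meeting and the therapeutic endoscopy, and restricts database access to two data handlers. The name and date could be added after scoring.
- How masking is done is often left to laboratory instructions, which are not at hand.

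All of this stands, and it rules out saying that the blind is broken. It does not secure the blind either. The form is the source record, it has a signature line for the pathologist, and nothing in the protocol tells staff to withhold the header or randomise the reading.

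A reader might also infer that every patient gives exactly two samples, so that order is always exposed. The protocol does not support that. Phase I patients may enter Phase II, patients who leave before the second endoscopy give one sampling only, and each endoscopy takes two histology biopsies. Nor is histology the trial's only protected or objective measure: 16S sequencing is also declared blinded, and laboratory values are outcomes. The point is confined to the PDAI.

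The size can be challenged too. A full point of average drift on a 0–6 score is large, and at a quarter point the effect nearly vanishes. The protocol names no test for the primary outcome, openly admits the open-label scoring, and says the trial cannot settle efficacy. These are fair limits on the size, but they do not bear on the conflict between the blinding claim and the form.

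**Conclusion.** The point holds in a limited form. The protocol asserts a blind reading and draws a no-bias conclusion from it, while its own source form carries information that can put one patient's samples in order. No described procedure prevents that. The passages on bias, histology, sample storage and the histology form need to be reconciled.

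It would go too far to say that the histological PDAI is unprotected or that the Phase II result would be biased. The header date is undefined, and the documents do not show what the pathologist actually receives.

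The size is illustrative and rests wholly on the assumed drift, SD and test. At n = 12 and SD 2 to 3, the false-positive rate moves from about 4–5% to about 7–11% for a half-point drift and about 16–33% for one point, allowing for either way of handling whole-point scores at the upper end. The case for correction does not depend on these figures. It rests on the contradiction and on how little it costs to remove. It should be corrected before the first slide is scored.

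**What to change.** On Appendix 6, replace name and date with a random specimen number unrelated to patient or visit order, and hold the link outside pathology. After the follow-up endoscopy, have each patient's before and after slides scored for the PDAI together, in random order, under those numbers. Join scores to time points only once scoring is complete.

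The Histology paragraph also asks for a descriptive report, including dysplasia and granulomas. Issue it without delay but under the same masked number, so that a reader who later scores the PDAI stays blind. If the laboratory cannot do this, remove the no-bias conclusion from the Bias paragraph and describe histology as not reliably masked.

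The cost is a form edit, relabelling, someone outside pathology to hold the link, and a baseline histology score about one week later in Phase I and two weeks later in Phase II. Dosing is not held up, because the drug is first applied at the same endoscopy as the biopsies. No visit, biopsy, reader or patient is added, and sample size and significance level are unchanged.

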## Appendix 7 – Patient PDAI overview

Patient name:

Criteria	Score	Patient score before treatment Date:    /    /   	Patient score after treatment Date:    /    /   
Clinical			
Stool frequency Usual postoperative stool frequency 1-3 stools/day > than postoperative usual >3 stools/day > postoperative usual	0 1 2		
Rectal bleeding None or rare Present daily	0 1		
Fecal urgency or abdominal cramps None Occasional Usual	0 1 2		
Fever (temperature > 37.8) Absent Present	0 1		
Endoscopic inflammation Edema Granularity Friability Loss of vascular pattern Mucous Exudate Ulceration	1 1 1 1 1 1		
Acute histological inflammation Polymorphonuclear leucocyte infiltration Mild Moderate + crypt abscess Severe + crypt abscess Ulceration per low power field (mean) <25% 25-50% >50%	1 2 3 1 2 3		
Total	18		

Date                      Place

Examiner:

Appendix 8 – Follow-up Day 7/14/(30/37)

Name:

Side effects:		
GM-CSF  Fever  Myalgia  Malaise  Abdominal pain  Diarrhea  Rash  Chest pain  Weight loss  Nausea  Vomiting  Peripheral edema  Dyspnea  Hypoxemia  Hypotension  Tachycardia  Flushing  Metabolic disease  Hyperbilirubinemia  Cardiac dysrhythmia  Pharyngitis	Metronidazole  Nausea  Glossitis  Dry mouth  Dysgeusia  Stomatitis  Myalgia  Candida-infection  dark urine	Fosfomycin  Phlebitis  Vomiting  Abdominal pain  Diarrhea  Rash  Fatigue  Dysgeusia  Decreased appetite  Vertigo  Headache
Adverse reactions           		
Serious adverse reactions / Life-threatening adverse reactions  Capillary leak syndrome           		

Protocol code no: 2020-01-GMF-1  
EudraCT no: 2020-000609-10

Clinical PDAI to be filled in at follow-up:

Criteria	Score	Patient score
Clinical		
Stool frequency		
Usual postoperative stool frequency	0	
1-4 stools/day > than postoperative usual	1	
>3 stools/day > postoperative usual	2	
Rectal bleeding		
None or rare	0	
Present daily	1	
Fecal urgency or abdominal cramps		
None	0	
Occasional	1	
Usual	2	
Fever (temperature > 37.8)		
Absent	0	
Present	1	
Total	6	

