## 2. Background and scientific rationale

The surgical procedure of choice for patients with therapy-resistant UC (ulcerative colitis) is proctocolectomy with IPAA (ileal pouch anal anastomosis) (1). The intent of the procedure is a definitive cure of the disease and reduction of the risk of developing malignancy while preserving continence.

Pouchitis, inflammation of the mucosa of the ileoanal reservoir, is one of the most common complications after IPAA. (2) Symptoms of pouchitis include hematochezia, increased stool frequency and urgency, abdominal cramping, pain, nausea, incontinence and fever, as well as extraintestinal manifestations. Endoscopy typically shows the mucosa to be erythematous, with friability and loss of vascular patterns. Histology shows signs of inflammation and extravasation of red blood cells in the lamina propria. Interestingly, the incidence of pouchitis is about 10 times lower in patients after IPAA in FAP (Familial adenomatous polyposis) (7). Various scoring systems have been developed to assess the severity of inflammation in pouchitis, of which the PDAI (Pouchitis Disease Activity Index) is the most common. It assesses clinical, endoscopic and histological features (8) (see Table 1 in Appendix 1).

Pouchitis can be further categorized into acute and chronic pouchitis.

- Acute pouchitis – duration <4 weeks
- Chronic pouchitis – duration >4 weeks despite therapy

The incidence of acute pouchitis has been reported to be up to 50% at 5 years and there is no official consensus on treatment (9,10).

Treatment includes oral antibiotics, most often with metronidazole and/or ciprofloxacin. The standard treatment at Zealand University Hospital for acute pouchitis consists of a 10-day treatment period with oral metronidazole or ciprofloxacin. Metronidazole, while effective, can cause nerve damage after prolonged use in high doses. As patients often experience repeated flare-ups of acute pouchitis or chronic pouchitis, this risk increases due to repeated and lengthy use (11).

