## Phase II – Proof of concept study

### Primary outcome measure

- Change in the pouchitis disease activity index (PDAI) – A decrease of 3 points or more will be determined as an improvement in PDAI from before application of the study drug to 7 days after application of the study drug

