## 8. Statistical considerations

We plan to include 6 patients in the Phase I study to test tolerability, and 12 patients in the Phase II study to test effectiveness of the treatment. The trial will end with the last visit of the last patient (Day 37 of the last patient). This is a safety and clinical proof-of concept intervention study, and we are, to the best of our knowledge, the first group to look into local treatment with GM-CSF and antibiotics of biofilm in patients with pouchitis after IPAA for ulcerative colitis. We expect this number of patients to be sufficient to provide the necessary experience in implementing the technique and form a basis for future studies, including future sample size calculation. This is based on calculations on number of patients required to achieve statistical significance of paired before-and-after comparisons by non-parametric tests. To achieve statistical significance at 1% level in Phase II, 9 patients are needed. As there is a risk of patients withdrawing from the trial prematurely or not receiving all interventions, we aim to include 3 additional patients.

Our primary objective is to test for adverse events or reactions in Phase I and a significant change in PDAI in Phase II, defined by a decrease of 3 points. Differences pre- and post-treatment will be described by means and standard deviations, or median and range when appropriate, and will be analyzed by the appropriate statistical tests. All patients described in chapter 5 as 'Completed test persons' will be included in the statistical analysis.

Microbial diversity changes will be analyzed using PERMANOVA (permutational analysis of variance). Other secondary objectives like change in WBC and CRP will be analyzed using the appropriate statistical tests.

Data will be analyzed using non-parametric or parametric statistics depending on the distribution of the data. P-values  $\leq 0.05$  are considered significant. Correction for multiple comparisons will be performed if needed. Descriptive statistics will be used for baseline characteristics.

Missing data will be handled depending on the type of data missing. If missing data results in a patient not being able to be defined as a 'Completed test person' (Chapter 5), the patient is excluded from the trial and a new patient will be recruited. If individual results are missing (e.g. laboratory values), the last known values will be used for analysis.

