## Appendices

### Appendix 1 – PDAI

Criteria	Score
Clinical	
Stool frequency	
Usual postoperative stool frequency	0
1–2 stool/day >postoperative usual	1
≥3 stools/day >postoperative usual	2
Rectal bleeding	
None or rare	0
Present daily	1
Faecal urgency or abdominal cramps	
None	0
Occasional	1
Usual	2
Fever (temperature >37.8°C)	
Absent	0
Present	1
Endoscopic inflammation	
Oedema	1
Granularity	1
Friability	1
Loss of vascular pattern	1
Mucous exudate	1
Ulceration	1
Acute histological inflammation	
Polymorphonuclear leucocyte infiltration	
Mild	1
Moderate+crypt abscess	2
Severe+crypt abscess	3
Ulceration per low power field (mean)	
<25%	1
25–50%	2
>50%	3

Table 1: Pouchitis Disease Activity Index (PDAI). A score of 7 or higher is diagnostic of pouchitis.

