### Appendix 3 – Enrollment form

Name:

Address:

Telephone no:

Date of birth
Gender
Year diagnosed with ulcerative colitis
Year of IPAA surgery
Allergies
Past medical history  COPD  Others  Diabetes  Asthma  Hypertension  Ischemic heart disease  Liver disease  Neurological diseases
Medicine
Past medicine used for pouchitis  Metronidazole  Ciprofloxacin  Ampicillin  Piperacillin  Probiotics  Others
Diets used for pouchitis

Protocol code no: 2020-01-GMF-1  
EudraCT no: 2020-000609-10

Clinical PDAI to be filled in at enrollment:

Criteria	Score	Patient score
Clinical		
Stool frequency		
Usual postoperative stool frequency	0	
1-2 stools/day > than postoperative usual	1	
>3 stools/day > postoperative usual	2	
Rectal bleeding		
None or rare	0	
Present daily	1	
Fecal urgency or abdominal cramps		
None	0	
Occasional	1	
Usual	2	
Fever (temperature > 37.8)		
Absent	0	
Present	1	
Total	6	

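### The PDAI stool-frequency item is printed with four different cut-off sets, so a patient unchanged at 3 or 4 extra stools a day can score 1 point better on the follow-up form than at enrolment

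*Protocol*

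**What the plan says.** The stool-frequency item of the PDAI appears four times in the Protocol, each time with different cut-offs for extra stools per day above the postoperative usual:

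- Appendix 1, the table to which Section 2 refers for the index: 1-2 scores 1, and "≥3 stools/day >postoperative usual" scores 2.
- Appendix 3, the enrolment form: "1-2 stools/day > than postoperative usual" scores 1, and more than 3 scores 2.
- Appendix 7, the before-and-after overview: "1-3 stools/day > than postoperative usual" scores 1, and more than 3 scores 2.
- Appendix 8, the follow-up form: "1-4 stools/day > than postoperative usual" scores 1, and more than 3 scores 2.

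On where the data come from, Section 9 states: "Appendix 3-6 and 8 are considered CRF on which source data is directly recorded". Appendix 7 is not in that list.

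For the Phase II primary outcome, and a Phase I secondary outcome, Section 3 states: "A decrease of 3 points or more will be determined as an improvement in PDAI". Section 8 bases the sample size on "statistical significance of paired before-and-after comparisons by non-parametric tests".

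**The concern.** A paired change is interpretable only if both members of the pair are measured on the same scale. Here the enrolment score is taken from Appendix 3 and the follow-up score from Appendix 8, and these two forms disagree with each other and with Appendix 1 at the boundary counts. Appendix 3 has a gap at exactly 3, and Appendix 8 has an overlap at exactly 4.

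For a patient whose stool frequency does not change, any error between the two forms lowers the follow-up score, which reads as benefit. The trial is open-label with a single arm, and the bias statement in Section 3 says only pathology and 16S sequencing are blinded. The person who resolves the gap or the overlap therefore knows the visit and the treatment. Neither clinical PDAI form has a field for the raw stool count, so a wrong score cannot be put right from the form.

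At stake are the size of the PDAI change and the classification of patients as improved. One false point is a third of the 3-point threshold. Section 3 applies the same threshold to the clinical subscore, whose maximum is only 6.

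**Working it through.** **Inputs.** The four cut-off sets in Appendices 1, 3, 7 and 8; the 3-point threshold in Section 3; 12 Phase II patients in Section 8. The printed maxima reproduce: the clinical score is 2 + 1 + 2 + 1 = 6 and the total is 6 + 6 + 6 = 18.

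**Step 1: score each count on each version.**

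| Extra stools/day | App. 1 | App. 3 | App. 7 | App. 8 |
|---|---|---|---|---|
| 0 | 0 | 0 | 0 | 0 |
| 1 or 2 | 1 | 1 | 1 | 1 |
| 3 | 2 | no row | 1 | 1 |
| 4 | 2 | 2 | 2 | 1 or 2 |
| 5 or more | 2 | 2 | 2 | 2 |

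The four versions differ only at 3 and 4.

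**Step 2: unchanged patient, Appendix 3 score minus Appendix 8 score.**

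- At 3: enrolment is 1 or 2, depending on how the assessor fills the gap, and follow-up is 1. The apparent fall is 0 or 1.
- At 4: enrolment is 2 and follow-up is 1 or 2. The apparent fall is 0 or 1.
- At 0-2 and at 5 or more: the apparent fall is 0.

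**Step 3: any pair of counts, compared with Appendix 1.** The error in the fall is (App. 3 − App. 1 at enrolment) + (App. 1 − App. 8 at follow-up). The first term is 0 except at enrolment 3, where it is −1 or 0. The second term is +1 at follow-up 3, 0 or +1 at follow-up 4, and 0 elsewhere. Over the 9 × 9 = 81 pairs of counts from 0 to 8:

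- A false gain is possible in 9 + 9 = 18 pairs (follow-up 3 or 4).
- It is certain in 8 pairs: follow-up exactly 3 from any enrolment value other than 3. A fall from 4 or more to 3 scores 2 then 1 on the forms, but 2 then 2 by Appendix 1. A rise from 1 to 3 scores 1 then 1, but 1 then 2 by Appendix 1, so a worsening is hidden.
- A false loss is possible in 8 pairs, all with enrolment exactly 3 and a different follow-up count.

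**Step 4: Appendix 7 at both visits.** An unchanged patient has no error, but a fall from 4-8 to 3 still scores 2 then 1, the same false point.

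**Step 5: size.** The Protocol does not give the share of patients at 3-4 extra stools. Assume 10%, 25% or 50% are there at both visits and, separately and independently, that 25% have a true 2-point fall. The lower bound is 0 in every case (matching rows ticked). The upper bounds, with the artefact in every such patient, are:

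| Share at 3-4 | Mean bias = share × 1 point | False responders = 12 × share × 0.25 | Response-rate error |
|---|---|---|---|
| 10% | 0.10 | 0.3 | 2.5 points |
| 25% | 0.25 | 0.75 | 6.25 points |
| 50% | 0.50 | 1.5 | 12.5 points |

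One misclassified patient is 1/12 = 8.3 percentage points.

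**Step 6: illustration for a paired test.** The Protocol names no test, so take a two-sided sign test with all k non-tied pairs improving: p = 2 × 0.5^k. This gives k = 5: 0.0625; 6: 0.031; 7: 0.0156; 8: 0.0078. The exact signed-rank test gives the same values in this situation. One patient with no true change who gains the false point moves k from 5 to 6 (across 0.05) or from 7 to 8 (across the 1% level used for sizing).

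**The case against.** - **Assessor choice.** For an unchanged patient the artefact depends on which row is ticked. At exactly 3, an enrolment score of 2 means ticking a row that says more than 3. At 4, the follow-up form equally allows the correct 2. This stands, and it is why the claim is that the score can differ. It does not touch the errors at follow-up exactly 3, which need no choice.
- **Electronic capture.** Section 9 limits paper sheets to the recruitment meeting and the therapeutic endoscopy and sends all other data straight to Easytrial. The clinical evaluations part of Section 7 also describes direct entry. The follow-up score may therefore be captured in a field with different wording. This stands as a limit: the finding concerns the printed forms, which Section 9 nevertheless calls CRFs.
- **Text extraction.** If more than 3 on the forms was really 3 or more, Appendix 3 would agree with Appendix 1, and the error at follow-up 3 would no longer be certain. But enrolment would score 2 at both 3 and 4 while follow-up still permitted 1 at both, so the mismatch survives.
- **Appendix 7 as remedy.** It is not a named source form, holds no raw count and contradicts Appendix 1 at exactly 3.
- **Size.** The error is at most 1 of 18 points, the assumed shares have no support in the Protocol, and the sign-test steps require that nobody worsens. Section 10 also says the trial cannot settle efficacy. All true, and the figures are bounds and illustrations. But the fault lies in the instrument for the primary endpoint, and the sequence 1-2, 1-3, 1-4 looks more like a transcription slip than a choice worth defending.

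**Conclusion.** The concern holds. As printed, the enrolment and follow-up forms do not measure stool frequency on the same scale, and neither matches Appendix 1. For an unchanged patient at 3 or 4 extra stools a day the change can be wrong by 1 point, and only in the direction of benefit. Where the follow-up count is exactly 3 and the enrolment count was anything else, a 1-point error towards benefit is certain against Appendix 1. Where the enrolment count is exactly 3 and the frequency changes, an error the other way is possible.

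The error cannot create a 3-point improvement on its own. It can turn a true 2-point fall into one, at 8.3 percentage points per patient in 12. Under the assumed shares of 10% to 50%, the mean change for patients with stable stool frequency is biased by between 0 and at most 0.10 to 0.50 points. These figures leave out the certain errors at follow-up exactly 3, because the Protocol gives no distribution of stool counts from which to size them. The discrepancy between the printed forms is certain; how far it biases recorded scores depends on the Easytrial wording and on assessor behaviour. Because it affects the primary endpoint of a small uncontrolled trial, it should be corrected before the forms are used further.

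**What to change.** Print the Appendix 1 stool-frequency categories (1-2 scores 1; 3 or more scores 2) identically in Appendices 3, 7 and 8, and check that the Easytrial fields carry the same wording. Add one field at each visit for the raw number of stools per day above the postoperative usual, so that the score can be verified.

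For any patient already scored on the current forms, re-score both visits by Appendix 1 where the count can be recovered from source records. Where it cannot, flag the item and report a sensitivity analysis of the PDAI change and of the 3-point response over the scores the forms allow.

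The cost is corrected CRF pages, matching database fields and one extra number per visit. No extra patients or procedures are needed.
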